**AN INVESTIGATION INTO THE RELATIONSHIP BETWEEN HEMORRHOID
DISEASE AND THE USE OF SMARTPHONES IN THE LAVATORY**

Unique Protocol ID: 12/22/2017 – 051

Date: February 11, 2018

Statistical Analysis

All data will be analyzed using the SPSS package program (version 20). The data will consist of categorical, nominal, and continuous numerical variables. Frequency and percentage rates will be given for categorical and nominal variables. Following testing for normal distribution, variables with normal distribution will be expressed as mean \pm standard deviation, while those that do not exhibit normal distribution will be expressed as median and minimum – maximum values. The relationship between risk factor and outcome variable will be evaluated using the Chi-square test. The effect of smartphone use on the presence or absence of hemorrhoids will be analyzed using the Binary Logistic Regression method. Any difference in the degree of hemorrhoids with respect to the duration of exposure to the risk factors will be determined by ANOVA or the Kruskal-Wallis test. A *p*-value of less than .05 will be considered statistically significant.

Calculation of Sample Size

According to the results of the pilot study, 36.4% of the population with hemorrhoidal disease use a smartphone for at least 2 minutes while in the lavatory. In the control group, this percentage was only 13.2%. Since this is a case-control study, the investigators first calculated the number of cases required to calculate the prevalence of a group with hemorrhoidal disease as per the below:

$$n = \frac{Z^2 p(1-p)}{d^2} \quad n = \frac{1.96^2 * 0.364(1-0.364)}{0.05^2} \quad N = 355.7$$

According to the above, in order to estimate a 5% difference in effect size, with an error rate of 5% and 80% power, at least 356 patients are needed. However, in this study, the sample for the logistic regression analysis needs to be calculated in order to investigate to what extent the use of a smartphone during defecation increases the risk of hemorrhoids.

According to analyses performed using the pilot study data, the percentage of the whole population who use a smartphone for at least 2 minutes while in the lavatory is 26.9%. In the logistic regression analysis, in order to determine whether or not smartphone use during defecation (the independent variable) has an effect on the presence or absence of hemorrhoidal disease (the dependent variable), the approach suggested by Peduzzi et al. (1) is as per the below:

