$$N = 10 k / p$$

where

P = the rate of positive or negative events in the population

K = the number of independent variables.

$$N = 10 * (22 / 0.269) = 817.8$$

According to these calculations, calculating the prevalence of smartphone use in the lavatory among the hemorrhoid patient population and measuring the effect of this habit on hemorrhoid development requires 818 patients and the same number of controls. Taking into account the possibility for incomplete or incorrect questionnaires by adding 10% loss to this figure results in a total of $818 + 81 = 899$ participants needed.

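### The events-per-variable calculation uses the pilot rate of smartphone use (26.9%) where the SAP's rule calls for the rate of the outcome, so 818 and 899 do not follow from that rule

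*SAP*

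**What the plan says.** All the SAP statements are in Calculation of Sample Size.

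- **Roles of the variables.** Smartphone use during defecation is the independent variable. The outcome is "the presence or absence of hemorrhoidal disease (the dependent variable").
- **The rule.** N = 10k/p, where K counts the independent variables and "P = the rate of positive or negative events in the population".
- **The input.** From the pilot, "the percentage of the whole population who use a smartphone for at least 2 minutes while in the lavatory is 26.9" per cent. The group rates are 36.4% in those with hemorrhoidal disease; "In the control group, this percentage was only 13.2" per cent.
- **The result.** "N = 10 * (22 / 0.269) = 817.8".
- **Its use.** The SAP gives the number two aims: "calculating the prevalence of smartphone use in the lavatory among the hemorrhoid patient population and measuring the effect of this habit on hemorrhoid development". Meeting both of them, in its words, "requires 818 patients and the same number of controls". It then adds 10% for unusable questionnaires (818 + 81) and calls the resulting 899 a total.
- **An earlier step.** A precision formula for smartphone use among cases gives "at least 356 patients are needed".

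The Protocol (Study protocol, methods, and procedures) recruits the study group on complaints of hemorrhoids and records their presence or absence at a later examination. It also says that the sample size will be based on the frequency of smartphone use in the two groups, with type I error 0.005 and 80% power.

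**The concern.** The 10-events rule asks for enough people in the rarer of the two outcome classes to support the number of predictors in the model. Here the classes are hemorrhoids present and absent. The share of people who use a smartphone in the lavatory describes a predictor and says nothing about how many fall into either class. No outcome rate enters the calculation.

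This line alone produces 818, and 899 follows from it. The SAP therefore has no valid derivation for the size of its main regression. The target is also unclear: someone running recruitment cannot tell whether to stop at 899 people or at about twice that number.

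**Working it through.** **Inputs.** From the SAP: k = 22 (stated, but the variables are not listed), 0.269, 0.364, 0.132, 356 cases, and 10% loss. From the Protocol: type I error 0.005 and 80% power.

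**1. The SAP's figure.** 10 × 22/0.269 = 817.8, rounded up to 818. It reproduces, so the fault lies in what 0.269 stands for.

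**2. What 0.269 is.** If it pools the two pilot groups with case share w, then 0.364w + 0.132(1 − w) = 0.269. So w = (0.269 − 0.132)/(0.364 − 0.132) = 0.137/0.232 = 0.5905. A pilot with about 59% cases and 41% controls gives exactly this pooled exposure rate. Equivalently, 818 × 0.269 = 220: the SAP's N secures 220 smartphone users, not 220 outcome events.

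**3. The rule with an outcome share as P.** The smaller class needs 10 × 22 = 220.

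| Smaller outcome class | Basis | Total N |
|---|---|---|
| 0.50 | 1:1 cases to controls | 220/0.50 = 440 |
| 0.45 | assumed | 220/0.45 = 488.9, so 489 |
| 0.40 | assumed | 220/0.40 = 550 |
| 0.4095 | control share implied in step 2 | 220/0.4095 = 537.3, so 538 |

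818 in total falls short of the rule only if the smaller class is below 220/818 = 26.9% of the sample.

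**4. Events per variable at 1:1.**
- 818 in total: 409/22 = 18.6.
- 899 in total, less 10% loss: 899 × 0.9 = 809.1, and 809.1/2/22 = 18.4.
- 818 per group: 818/22 = 37.2.

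**5. The two readings of the target.**
- Before loss: 818, or 2 × 818 = 1636.
- With the SAP's loss allowance: 899, or 2 × 899 = 1798.

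The ratio is exactly 2 in each pair.

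**6. The other stated aims.**
- Precision among cases: 1.96² × 0.364 × 0.636/0.05² = 355.7, so 356 cases. At 1:1, 818 in total holds 409 cases, and 809.1 after loss holds about 404. The requirement is missed only if confirmed cases fall below 356/818 = 43.5% of the sample, or 356/809.1 = 44.0% after loss.
- Two-group comparison (Protocol): 36.4% against 13.2% at two-sided 0.005 and 80% power (z = 2.807 and 0.842). With unpooled variance, n = (2.807 + 0.842)² × (0.364 × 0.636 + 0.132 × 0.868)/0.232² = 85.6, so 86 per group. With pooled variance under the null, n = 90.7, so 91 per group. Neither has a continuity correction.

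**The case against.** The best defence is that the wrong input does no visible harm. At 1:1 it raises the requirement from 440 to 818, and nothing in the documents points to a smaller class below 26.9%. That stands: the regression is not shown to be undersized. What remains is that the SAP credits a rule with a number that the rule does not give.

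It can also be said that the words about positive or negative events are loose enough to cover smartphone use. They are not. The model is for presence or absence of hemorrhoids, so those are its two event classes, and smartphone use is one of the variables that K counts.

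A reader might infer three stronger things that the documents do not support:

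- **The study is too small.** Steps 3 and 4 show the opposite at 1:1. The outcome share could differ from the recruitment ratio, because hemorrhoids are confirmed only at examination, but no confirmation rate is given.
- **The study should shrink to 440.** The SAP's final number also serves the prevalence aim. With 220 cases the half-width would be 1.96 × √(0.364 × 0.636/220) = 0.064, not the SAP's 0.05.
- **The target should become 712 (356 per group).** That figure depends on keeping 1:1: 356 cases with 220 controls, 576 in all, would meet both rules. It also rests on a 356 that the SAP describes as having 80% power, although its formula has no power term. It illustrates the precision aim and is not a recommended target.

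**Conclusion.** The concern holds as an error of justification. P was filled with the prevalence of an exposure, so 818 and 899 do not follow from the SAP's stated rule. With k = 22 as stated, the rule gives 440 in total at 1:1 and about 538 at the implied pilot mix. The stated size exceeds both, and no shortfall is shown.

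The factor-of-two ambiguity in the target is a separate fault in the same paragraph. It carries the greater practical consequence, but correcting P would not remove it.

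The magnitudes rest on k = 22, on 26.9% being a pooled rate of the two pilot groups, and on an outcome split near 1:1. The central point rests on none of these. Ten events per variable guards model stability; it is not a power calculation for the adjusted smartphone effect.

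**What to change.** In the SAP, Calculation of Sample Size:

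1. Replace 0.269 with the expected share of the smaller outcome class, stated as an assumption (0.5 at 1:1). Present the result as a total N, and do not present 818 as the number that the 10-events rule requires.
2. State one recruitment target, per group and in total, with the loss allowance applied to it. It replaces both the per-group use of 818 and the total of 899.
3. If the existing size is kept, say so and report what it delivers at 1:1: about 18 events per variable if 818 or 899 is the total, about 37 if 818 is per group. Add that at 1:1 it covers the 356 cases (on the total reading, while confirmed cases are at least about 44% of the sample) and the Protocol's two-group comparison at 0.005 (about 86 to 91 per group).

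The cost is SAP wording and a restated number. No extra participants are needed at a 1:1 outcome split; on the 899-total reading this holds subject to the 44% condition in item 3.

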The study population consists of patients with complaints of hemorrhoids referred to the General Surgery Polyclinic. The control group is comprised of healthy volunteers with no complaints of hemorrhoids (Figure 3). Both the study group and the control group will include persons of both genders between 16 and 65 years of age. Informed consent will be obtained from patients and volunteers, following which a Likert-type survey will be given to each participant to complete (Table 1, questionnaire form). A pilot study will be conducted for the factor analysis of the questions to be asked in the questionnaire. In the pilot study, the target will be to survey 100 patients. After the factor analysis is performed on 100 patients, the questionnaire that is developed will be used in the main study.

As no prevalence study was previously performed for the sample size, it will be calculated based on the prevalence (frequency of smartphone use in the lavatory in the study group and the control group) determined after the pilot study, accepting a type I error of 0.005 and a type II error of 0.20 (80% test power).

The doctor who performs the examinations will be blinded to the questionnaire results. After completion of the questionnaire, the patient's anal region and rectum will be examined by a general surgeon and the presence or absence of hemorrhoids will be noted. Subsequently, if hemorrhoids are present, they will be recorded as either external or internal. Internal hemorrhoids will then be staged as first-degree, second-degree, third-degree, or fourth-degree, according to standard textbook definitions [2].

Primary endpoints of the study:

1) determination of the stage of hemorrhoids in patients with complaints of hemorrhoids

Tarih :

Versiyon :

2) frequency and duration of smartphone use in the lavatory for those with smartphones

Statistical Data Analysis:

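### The SAP asks for 818 patients plus as many controls (1,636 people), then gives 899 as the total after loss, so the recruitment target is undefined by a factor of two

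*SAP*

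**What the plan says.** All main-study numbers are in the SAP, Calculation of Sample Size. A precision formula for smartphone use among patients first gives "at least 356 patients are needed". The SAP then moves to a second calculation for the logistic regression, which drives the final target.

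That calculation uses N = 10k/p, with k the number of independent variables (22) and p defined as follows: "P = the rate of positive or negative events in the population". The value entered for p is 0.269, taken from the pilot: "the percentage of the whole population who use a smartphone for at least 2 minutes while in the lavatory is 26.9" per cent. The result is "N = 10 * (22 / 0.269) = 817.8".

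Two sentences then turn this into a target:

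- The study "requires 818 patients and the same number of controls".
- An allowance of 10% for unusable questionnaires is put on top of one 818, which "results in a total of $818 + 81 = 899$ participants needed".

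The Protocol, under Study protocol, methods, and procedures, gives neither a main-study number nor a case-to-control ratio. Of the sample size it says "it will be calculated based on the prevalence" found in the pilot. The 100 given there is the pilot target.

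**The concern.** The first sentence sets a requirement of 818 in each of two groups. The second gives a total that already includes the loss allowance, yet it is far below that requirement before any loss. One of them must be wrong as worded.

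The formula does not explain the doubling either. The SAP's dependent variable is the presence or absence of hemorrhoids, so patients and controls enter one model and N in 10k/p counts all records in it. A second 818 for controls does not follow from the calculation.

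This is the only recruitment target in the documents. As it stands, nobody can say when recruitment is complete or later judge whether the target was met. If 899 is the overall total, the SAP claims about twice the per-group size that it will have.

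**Working it through.** **Inputs (all from the SAP, Calculation of Sample Size).** k = 22; p = 0.269; pilot smartphone use 36.4% in the hemorrhoid group and 13.2% in controls; loss 10%. The 1:1 split below is stated only through the equal-controls clause. It becomes an assumption if that clause is dropped.

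**1. Reproduce the SAP's figures.**
- 10 × 22 / 0.269 = 817.8, rounded up to 818.
- 10% of 818 = 81.8, cut to 81; 818 + 81 = 899.

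Both reproduce, and 899 comes only from a single 818.

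**2. Apply the same steps to the requirement as worded.**
- 818 + 818 = 1,636 before loss.
- With the SAP's own allowance, 2 × 899 = 1,798.
- 1,636 − 899 = 737, so the stated total after loss is 737 people below the requirement before loss (899/1,636 = 55.0%). Like for like, 899/1,798 = 50%.

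**3. What each reading delivers (1:1 split, 10% loss).**

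| | 899 overall | 899 per group |
|---|---|---|
| People recruited | 899 | 1,798 |
| Evaluable per group | 899 × 0.9 / 2 = 404.6 | 899 × 0.9 = 809.1 |
| Share of the stated 818 | 49.5% | 98.9% |
| 95% CI half-width, smartphone use among patients: 1.96 × √(0.364 × 0.636 / n) | 4.7 points | 3.3 points |
| Events per variable, n/22 | 18.4 | 36.8 |
| Unadjusted OR at pilot rates, Woolf 95% CI | 3.76 (2.65 to 5.35) | 3.76 (2.93 to 4.83) |

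The OR is (0.364/0.636) / (0.132/0.868) = 3.76. It is unadjusted and shown only to compare precision.

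**4. Dependence on the split.** With 899 overall, 809.1 people are evaluable. Reaching 356 patients needs a patient share of at least 356/809.1 = 44%. At an assumed one patient to two controls there would be 809.1/3 ≈ 270.

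**5. Why 818 is not a safe base for a corrected figure.** The SAP defines p as an event rate, and the event in this model is hemorrhoidal disease. The 0.269 is the prevalence of the exposure. The same rule with an event rate gives:
- assumed 1:1 split, p = 0.5: 220/0.5 = 440 in total;
- case share w implied by the pilot, if the 26.9% pools pilot patients and controls: 0.364w + 0.132(1 − w) = 0.269, so w = 0.137/0.232 = 0.59. Using the rarer outcome, 220/0.4095 ≈ 537 in total (532 to 543 allowing for rounding of the percentages).

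**The case against.** The best defence is that 818 is not ambiguous at all: the SAP explicitly asks for that many patients and as many controls, which also states a 1:1 ratio. On this view the loss sentence inflates one group's figure, and its word for the total means only the sum 818 + 81. Then 899 is per group and one word is badly chosen. This is a fair reading, but it does not remove the defect. The sentence calls 899 a total of participants, so it still has to be corrected, to 1,798. Nor does the formula support it, since N there is the combined sample. The documents favour neither sentence conclusively.

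A second objection is that the reassurance about 356 counts every enrolled patient as a case. The Protocol recruits people with complaints and then records on examination whether hemorrhoids are present. If about 12% of 404.6 patients had none, confirmed cases would fall to about 356 (404.6 × 0.88 = 356), and no confirmation rate is given. This stands as a caveat. The SAP words its 356 as patients, so its own requirement is met as written, and 18.4 events per variable leaves ample room above 10.

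A third objection is that the choice of p and the way loss is added are separate matters. That is so. They matter here only because a corrected target should not carry 818 forward as if it were soundly derived.

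**Conclusion.** The contradiction holds. The SAP's one recruitment target takes two values a factor of two apart, 899 or 1,798, and neither document resolves it. If 899 is overall, the per-group size that the SAP can claim falls from 818 to about 405, given a 1:1 split, 10% loss in each group and every enrolled patient counted as a case.

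Neither reading shows inadequate power or precision on those assumptions. The fault is an undefined target and, on one reading, an overstated group size. It should be fixed, but it does not by itself threaten the analysis.

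**What to change.** The sponsor should first confirm which figure was intended. The SAP should then say whether 818 and 899 are overall or per group, give the case-to-control split, and correct the sentence that does not match.

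- **If 899 is the total:** delete the clause asking for as many controls, and state what 899 delivers at the chosen split. At 1:1 after 10% loss that is about 405 per group, a half-width of about 4.7 points and about 18 events per variable. The cost is SAP wording only, plus the lower per-group claim.
- **If 899 is per group:** correct the total to 1,798. The stated total then doubles, so the text should not be changed this way without confirmation.

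In neither case should 409 + 409 be written in as a derived requirement. If the events-per-variable rule is kept as the justification, enter the event rate and not the prevalence of smartphone use, and show the result (440 or about 537 in total under the assumptions above).

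A minor note: adding 10% leaves 809 after loss (899 × 0.9) against the 818 wanted; dividing by 0.9 gives 909.

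### The SAP asks for 818 patients and 818 controls but inflates 818 only once and gives 899 as the total, so its final figure contradicts its own requirement; the 10% allowance is also slightly short

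*SAP*

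**What the plan says.** The protocol gives no sample size. It defers the number to the pilot study. The only final figure is in the SAP under Calculation of Sample Size, and it is reached in three steps.

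- **Base number.** An events-per-variable rule with 22 independent variables gives "N = 10 * (22 / 0.269) = 817.8", taken as 818.
- **Requirement.** The SAP concludes that estimating prevalence and measuring the effect of the habit "requires 818 patients and the same number of controls".
- **Loss allowance.** The following sentence allows for questionnaires that cannot be used: "by adding 10% loss to this figure results in a total of" 818 + 81 = 899 participants.

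**The concern.** The requirement is stated for two groups of 818. The loss allowance is applied to one 818, and the result is called a total. A reader who wants to know how many people the study planned to enrol can take either 899 or twice that from adjacent sentences. Neither document says which is meant.

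The allowance also does not do quite what it is for. Its purpose is to have 818 usable questionnaires left after loss. Adding 10% of the required number is not the same as enrolling enough that 90% of those enrolled equals the required number, and here the added amount is rounded down as well.

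What is at stake is whether anyone can judge that the study reached its planned size. The first problem is a factor of two. The second is about 1%.

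**Working it through.** **Inputs, all from the SAP's sample-size section:** k = 22 variables; p = 0.269; base 818; equal numbers of patients and controls; 10% loss; stated result 899.

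**1. Reproduce the SAP's figures.**
- Base: 10 × 22 / 0.269 = 817.84, rounded up to 818. This matches.
- Allowance: 0.10 × 818 = 81.8, written as 81. Then 818 + 81 = 899. This matches only if 81.8 is truncated. Rounded up, the same additive method gives 900. The section rounds up elsewhere (355.7 to 356, 817.8 to 818).

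**2. Usable number required.** Read literally, 818 + 818 = 1,636.

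**3. What 899 yields if 10% of enrolled questionnaires are lost.** 899 × 0.90 = 809.1.

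| Reading | Enrolled | Usable after 10% loss | Required | Result |
|---|---|---|---|---|
| 818 per group, 899 overall | 899 | 809 | 1,636 | 809/1,636 = 49% |
| 818 per group, 899 per group | 2 × 899 = 1,798 | 1,798 × 0.90 = 1,618 | 1,636 | 18 short overall, 9 per group |
| 818 overall, 899 overall | 899 | 809 | 818 | 9 short |

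The first row takes both sentences as written. The second requires the word *total* to be wrong. The third requires the statement about an equal number of controls to be wrong.

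**4. The loss step alone.**
- Number that leaves 818 after 10% loss: 818 / 0.90 = 908.9, so 909. Check: 909 × 0.90 = 818.1, while 908 × 0.90 = 817.2.
- Largest loss that 899 can absorb and still leave 818: 81 / 899 = 9.0%.
- Shortfall at 10% loss: 818 − 809 = 9 usable questionnaires, 9/818 = 1.1%.
- If 10% instead means 10% of the required 818, then 899 − 81 = 818 and only the truncation remains (81 for 81.8).

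**The case against.** The strongest reply concerns the loss step. The SAP says that it adds 10% to the figure, and it does so. On that convention 899 returns 818, and less than one participant is at issue. Even on the other convention the gap is 1.1%, the 10% is a round allowance with no stated source, and the base is a rule of thumb rather than a power calculation. All of this stands, and it is why the loss step is the minor part of the point. It does not touch the conflict between two groups of 818 and a total of 899.

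A second reply is that N = 10k/p gives the size of the whole analysed sample, so the equal number of controls may be the slip and 899 overall may be what was intended. That is possible. It shows that one of the two sentences has to change, and the documents do not say which.

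Three stronger conclusions might be inferred, and the documents support none of them.

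- **That the shortfall takes the model below 10 events per variable.** Putting 809 into the SAP's formula gives 809 × 0.269 / 22 = 9.89. But 0.269 is the rate of exposure: "the percentage of the whole population who use a smartphone for at least 2 minutes while in the lavatory is 26.9" per cent. The dependent variable is hemorrhoidal disease. With equal groups about half the participants are events, so 809 overall gives about 404 / 22 = 18 per variable, and 809 per group gives 809 / 22 = 37. Neither is near 10.
- **That the correct target is 909 per group, 1,818 in all.** This assumes that 818 is a per-group number, which is exactly what is unsettled.
- **That the study lacks power.** No power target is attached to 818 or 899. For a simple comparison of the pilot proportions, 36.4% and 13.2%, the usual two-proportion formula at 80% power gives 54 per group at two-sided 0.05, and 91 at the 0.005 that the protocol names. Every reading above is well beyond that.

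**Conclusion.** The SAP is wrong as written. Adjacent sentences require 1,636 usable questionnaires and set a total of 899 enrolled, and no reading makes both correct. Taken literally, 899 delivers about 809 usable, 49% of the requirement. Taken as per group, the overall target of 1,798 appears nowhere. This conclusion needs only the SAP's own words and its 10% loss rate.

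The secondary point is small and conditional. If 10% is the share of enrolled questionnaires lost, which is the usual meaning of such an allowance but is not defined in the SAP, 899 leaves 809 rather than 818. If it is 10% of 818, only a rounding slip remains.

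The point is one of inconsistent reporting of the planned size. It does not show that the regression or the main comparison would be too small.

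**What to change.** 1. Reconcile the two sentences. State whether 818 and 899 are per group or overall, and give the overall enrolment target in one figure.
2. State the usable number that 899 yields after 10% loss (809 per group or 809 in all), in place of the implication that it secures 818. Say whether the 10% is of those enrolled or of those required.
3. If the target is recalculated rather than restated, use 818 / 0.90 = 909 for whichever unit 818 refers to.

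Items 1 and 2 cost a sentence or two of SAP text and can be done whatever the state of recruitment. The cost of item 3 depends on item 1. It is 10 more participants if 818 and 899 are both overall (909 − 899). It is 20 more if both are per group (1,818 − 1,798). If 818 is per group and 899 was meant as the overall total, recruitment roughly doubles, from 899 to 1,818. That last case is a design decision, not a text correction, and should not be made by default.
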